#### **B. Hypotheses / Research Question(s)**

We hypothesize that food supplemented with dietary fiber will reduce postprandial glycemic response as compared to a standard meal tolerance test (white bread with 50 g of available carbohydrates). Further, the impact of supplemented food, although with the same amount of dietary fiber, will vary due to differences in cooking procedures and serving temperatures.

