**GROUP ASSIGNMENT.** Upon confirmation of eligibility, the Research Officer will measure fasting blood glucose concentration (FBG) by performing a finger prick test (ACCU-CHEK® Aviva Plus, Roche Diabetes Care, Indianapolis, IN). Participants who are clinically diagnosed with impaired glucose tolerance or type 2 diabetes (diet-controlled and/or on oral hypoglycemic medications) will be assigned to the Prediabetes/Diabetes group irrespective of their finger prick test results. For participants who are not diagnosed with diabetes, those with FBG < 100 mg/dL will be assigned to the Non-Diabetes group, and those with FBG ≥ 100 mg/dL will be assigned to the Prediabetes/Diabetes group based on classification guidelines from the American Diabetes Association (5). Participants will also be asked to sign up for one of the testing panels: 1) Panel A will test one control food (white bread) and six fiber-supplemented food (dietary fiber mix in water, hot waffle, room temperature waffle, hot pancake, room temperature pancake and muffin); or 2) Panel B will test one control food (white bread) and six fiber-supplemented food (dietary fiber mix in water, sponge cake, crispbread, vegetable smoothie, fruit smoothie and muffin). Finally, the Research Officer will collect information to complete the participant profile, including anthropometry measurements (height and weight), and demographics and contact details.

The eligibility screening and group assignment visit will take approximately 1 h to complete.

**FOOD TESTING.** In the morning of each testing day, participants will attend IFNH between 8 and 10 am after an overnight fast of at least 8 h. They will be required to consume all the study food provided under supervision. The

amount of white bread to be consumed will contain 50 g of available carbohydrates (3-4 slices of bread), and the amount of fiber-supplemented food to be consumed will contain 60 g of dietary fiber mix (approximately 2 waffles, 2 pancakes, 2 slices of sponge cake, 2 serves of crispbread, 2 muffins or 300 ml of smoothies). Participants may leave the research facility after consuming the food, and they will be instructed to refrain from eating and drinking (except water) for the next 3 h. Each food will be tested twice over two consecutive days, with all testing to be completed in 4 weeks (Figure 1). Each food testing session will take approximately 30 min to complete.

[figure not shown]

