### 1.5 Sample Size Justification

No power calculation is performed for this pilot study. We aim to have 5 completers in the Non-Diabetes and 5 in the Prediabetes/Diabetes group, for each of the test panel (i.e. a total of 20 completers). This sample size is comparable to those used in published pilot studies on bran products. Steinert et al (7) used 10 participants (healthy, overweight and obese) to examine the effect of oat bran on glycemic response; Sheflin et al (8) used 7 participants (3 in control and 4 in experimental group) to examine the effect of heat-stabilized rice bran on gut microbiota and metabolites.

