### 1.6 Study Variables

#### A. Independent Variables, Interventions, or Predictor Variables

The independent variable will be type of food: white bread vs dietary fiber mix in water, waffle, pancake, sponge cake, crispbread, vegetable smoothie, fruit smoothie and muffin.

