#### **4.3 Subject Randomization**

Participants will not be randomized. They will be assigned to the Non-Diabetes group if their FBGs are < 100 mg/dL, and to the Prediabetes/Diabetes group if their FBGs are  $\geq 100$  mg/dL. At participant's choice, they will sign up to one of the two testing panels (see Section 1.3).

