#### **4.5 Number of Subjects**

##### **A. Total Number of Subjects**

24

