**C. Require Number of Subjects to Complete Research**

20 (5 each in Panel A Non-Diabetes group and Prediabetes/Diabetes group, same two groups for Panel B)

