**D. Feasibility Of Recruiting**

We expect to recruit the majority of our participants from the New Brunswick campus of Rutgers University. With a relatively flexible study schedule and no particularly stringent eligibility criteria, we do not anticipate difficulties in engaging interest in the Rutgers community. We expect a recruitment rate of 4-6 participants per week over 4-6 weeks including an estimated attrition rate of 20%.

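### Minor: 24 enrolled at 20% attrition gives about 19 completers, not the required 20 with 5 in each of four cells, and the ANOVA in 6.1 names no participant term although each person eats seven foods twice

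*Combined protocol and SAP*

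**What the plan says.** **Numbers.** Section 4.5, under "A. Total Number of Subjects", gives 24. Section 4.5C, headed as the number required to complete, gives "20 (5 each in Panel A Non-Diabetes group and Prediabetes/Diabetes group, same two groups for Panel B". Section 1.5 has the same target in softer words: "We aim to have 5 completers in the Non-Diabetes and 5 in the Prediabetes/Diabetes group, for each of the test panel". It also states that no power calculation was done. Section 4.5D gives a recruitment rate of 4–6 per week over 4–6 weeks, "including an estimated attrition rate of 20"%.

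**Allocation.** Nobody is randomized. Glycemic group follows from diagnosis or fasting glucose (1.3, Group Assignment; 4.3). Panel is chosen by the participant: "Participants will also be asked to sign up for one of the testing panels" (1.3) and "At participant's choice, they will sign up to one of the two testing panels" (4.3). No section states a cap, quota, panel-closure rule or replacement rule.

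**Foods and analysis.** Each panel has seven foods, each tested twice (1.3, Food Testing). White bread, fiber mix in water and muffin are in both panels. Section 1.6A treats food as a single factor: "The independent variable will be type of food: white bread vs dietary fiber mix in water, waffle, pancake, sponge cake", continuing through the rest of the foods. Section 6.1A names analysis of variance with Tukey's post-hoc test for comparisons within and between groups on area under the curve. It names no participant, repeated-measures or panel term.

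**The concern.** Enrolment, attrition and completer target are three figures from one section, and they should be mutually consistent. They are not, and the cell requirement makes the gap larger than the total suggests. A total near 20 can still leave one cell at 3 or 4, because neither margin of the two-by-two layout is controlled. Eight foods appear in one panel only and rest on a single cell per glycemic group, so a shortfall falls on them. They include the hot and room-temperature waffles and pancakes, which bear on the hypothesis that the impact of the food "will vary due to differences in cooking procedures and serving temperatures".

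The analysis point is separate and belongs to 6.1. The design is within-person for every food comparison inside a panel. An ANOVA with food as its only factor treats repeated results from one person as if they came from different people. The standard error of each food difference, and every Tukey comparison built on it, is then wrong.

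**Working it through.** **Inputs.** Enrolled 24 (4.5A). Completers 20 as 4 × 5 (1.5, 4.5C). Attrition 20% (4.5D). Seven foods × 2 tests = 14 results per person (1.3). Assumed, because the documents do not give them: independent dropout, panel preference and glycemic mix.

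**Step 1: the plan's 24.** 20 × (1 + 0.20) = 24 reproduces the figure. A 20% loss from those enrolled needs 20 / (1 − 0.20) = 25. The documents do not say how 24 was obtained.

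**Step 2: expected completers.** 24 × 0.80 = 19.2, and 19.2 / 4 = 4.8 per cell. The total falls short by 0.8 of a participant. Enrolling 24 yields 20 only if attrition is at most 1 − 20/24 = 16.7%.

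**Step 3: probability of the total.** With X ~ Binomial(24, 0.80), P(X ≥ 20) = 0.46. With 25 enrolled it is 0.62.

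**Step 4: probability of the cells, if each enrols exactly 6.** P(all four reach the threshold) = P(Binomial(6, 1 − attrition) ≥ threshold)⁴.

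| Attrition | P(total ≥ 20 of 24) | All cells ≥ 5 | All cells ≥ 4 |
|---|---|---|---|
| 10% | 0.91 | 0.62 | 0.94 |
| 20% (plan) | 0.46 | 0.655⁴ = 0.18 | 0.901⁴ = 0.66 |
| 30% | 0.11 | 0.03 | 0.31 |

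**Step 5: no cap or quota, 20% attrition.** With 12 per glycemic group and panel preference π for Panel A, the probability is [Σₖ Bin(k; 12, π) · P(Bin(k, 0.8) ≥ t) · P(Bin(12 − k, 0.8) ≥ t)]². If the glycemic mix is itself random at 50:50, the same product is averaged over the group sizes.

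| Assumption | All cells ≥ 5 | All cells ≥ 4 |
|---|---|---|
| 12 per group, 50:50 preference | 0.04 | 0.31 |
| Random 50:50 group mix, 50:50 preference | 0.02 | 0.21 |
| 12 per group, 70:30 preference | 0.007 | 0.09 |

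Both uncontrolled margins matter: leaving the glycemic mix free halves the first figure again.

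**Step 6: the missing participant term.** Take one panel with its 10 intended completers. If both tests of each food are entered, there are 10 × 14 = 140 values, and an ANOVA on food alone has 140 − 7 = 133 error degrees of freedom. If the two tests are averaged, there are 70 values and 70 − 7 = 63. With participant as a block on the averaged values, the error degrees of freedom are (10 − 1) × (7 − 1) = 54.

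The size of the error term changes too. Every participant in a panel eats every food in it, so differences between people cancel from a food difference. The unblocked error still contains them. With averaged tests it is therefore too large. With both tests entered separately, it is too large or too small according to whether variation between people exceeds variation in how people respond to particular foods. The documents give no variances, so the size of this error cannot be stated.

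**The case against.** **The gap is trivial in a pilot.** For the total this stands: 0.8 of a participant, with no stated power to lose. Section 1.5 speaks only of an aim, no completer-only analysis is stated, and a late dropout may still contribute foods already tested. The three shared foods draw on both panels, or 12 × 0.8 = 9.6 completers per glycemic group if 12 are enrolled in each. What remains is that 4.5C states 20, with 5 per cell, as the number required.

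**The 20% may not apply to the 24.** Section 4.5D attaches it to the recruitment rate, whose midpoint gives 5 × 5 = 25 and 25 × 0.8 = 20. That is a fair reading of 4.5D, but 4.5A still enrols 24. A reader might infer that 24 came from a wrong inflation formula. It fits that pattern, but the documents do not show it.

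**The cell probabilities rest on assumptions.** The free-choice figures do. The 0.18 needs no assumption about preference or mix, only 6 per cell and independent dropout at the plan's rate. At 10% attrition it would be 0.62.

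**Comparisons within groups may be meant as repeated measures.** Possibly, but no within-participant factor is written.

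**A stronger reading: self-selected panels confound the food comparisons.** A reader might infer this from the single food factor in 1.6A and a Tukey test over all foods. The documents do not support it as a flaw in the planned contrasts. The stated comparison is with white bread, which both panels eat. Hot against room temperature lies wholly within Panel A. Contrasts between cooking methods exist inside each panel. No cross-panel contrast is announced, although none is excluded.

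**Conclusion.** The point holds and is minor. As written, the size statement is inconsistent: 19.2 expected completers against 20 required, with a 0.46 chance of reaching 20 at the plan's own attrition. The cell requirement is the weaker part: 0.18 with perfectly even enrolment, and about 0.02 to 0.04 with free choice at 50:50 panel preference. The causes are the lack of any rule on panel and on glycemic group together, not panel choice alone. The arithmetic is certain. The free-choice figures are illustrations under stated assumptions. The shortfall invalidates no planned analysis or power claim.

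The missing participant term in 6.1 stands on its own, whatever the enrolment. It affects the error of every within-panel food comparison, by an amount the documents do not allow one to calculate.

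**What to change.** **1. Sections 1.5 and 4.5.** State 24 enrolled, about 19 expected completers, and 5 per cell as an aim rather than a requirement. This is wording only.

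**2. Sections 1.3 and 4.3.** Add: *Sign-up to a panel closes within a glycemic group once 6 participants of that group have joined it.* This keeps participant choice until a cell is full. It limits imbalance but does not fill cells: the 0.66 chance of at least 4 completers in every cell holds only if every cell enrols 6. The cost is that some participants lose their preferred panel, and some are turned away once both cells of their glycemic group are full. If the other group recruits slowly, enrolment could end below 24.

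**3. Section 6.1A.** Write: *Foods are compared within each panel (7 foods, 21 pairs) with participant as a blocking (repeated-measures) factor. The three foods common to both panels may also be compared across all participants with the same block. Any cross-panel comparison uses each participant's difference from white bread and is labelled exploratory.* The 21 is 7 × 6 / 2. This needs no extra data. Running by panel splits the shared foods, but their three mutual comparisons can still use everyone, because every participant is due to eat all three.

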##### **▪ Exclusion Criteria**

- Receiving insulin for diabetes treatment
- Receiving injectable prescription medicine
- Self-reported allergy or intolerance to any ingredients in the test food
- Any conditions deemed by the investigators that would prevent participation in the study, e.g. participation in past or active clinical research that may interfere with study outcomes, at the discretion of the investigators
- Any conditions deemed by the investigators that would compromise the individual's ability to complete the study, e.g. serious psychiatric conditions, at the discretion of the investigators

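### Participants choose their own panel, so any comparison of a Panel A-only food with a Panel B-only food is between self-selected people

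*Combined protocol and SAP*

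**What the plan says.** Section 4.3 states "Participants will not be randomized" and, of the panels, "At participant's choice, they will sign up to one of the two testing panels". Section 1.3 (Group Assignment) repeats this: "Participants will also be asked to sign up for one of the testing panels". The sign-up is described in the same paragraph as, and after, the fasting glucose step ("the Research Officer will measure fasting blood glucose concentration (FBG) by performing a finger prick test"), within a single visit of about an hour.

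The panels differ only in their foods. Besides white bread, Panel A tests "dietary fiber mix in water, hot waffle, room temperature waffle, hot pancake, room temperature pancake and muffin". Panel B also has white bread, the mix in water and muffin, but replaces the waffles and pancakes with sponge cake, crispbread, a vegetable smoothie and a fruit smoothie.

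The second hypothesis in Section 1.1 B is that "the impact of supplemented food, although with the same amount of dietary fiber, will vary due to differences in cooking procedures and serving temperatures". Section 1.6 A names one independent variable, type of food, and lists foods from both panels under it. Section 6.1 A analyses area under the glucose curve by ANOVA with Tukey's post-hoc test at a two-tailed 0.05. It mentions no panel term, no covariate and no expression of a food relative to the same person's bread. Sections 1.5 and 4.5 C set a target of 5 completers per glycemic group in each panel.

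**The concern.** A participant who picks between waffles and pancakes on one side and cake, crispbread and smoothies on the other may do so for reasons linked to glucose response, such as usual diet, weight, treatment or severity of diabetes. The 5-per-cell target balances the two glycemic categories across panels but not the people inside them. Under Section 1.3 the Prediabetes/Diabetes group runs from undiagnosed people with fasting glucose of 100 mg/dL or more to patients with type 2 diabetes on oral drugs.

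A difference between, say, pancake and sponge cake could then be a difference between the people who chose each panel. Nothing in the planned analysis separates the two; Tukey's test controls multiplicity, not confounding. Section 1.1 A says the pilot is meant to inform a later dietary intervention in type 2 diabetes, so a misleading contrast between foods could carry into that work.

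**Working it through.** **The plan's own figures.** Completers: 5 × 2 glycemic groups × 2 panels = 20, as in Sections 1.5 and 4.5 C. Enrolment: 20 × 1.20 = 24, as in Section 4.5 A with the 20% attrition of Section 4.5 D (20 / 0.80 would give 25). The method of panel allocation does not enter either figure.

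**Which pairs cross panels.** From the food lists in Section 1.3:
- Supplemented foods: 2 shared (mix in water, muffin) + 4 A-only + 4 B-only = 10. Pairs: 10 × 9 / 2 = 45. A-only with B-only: 4 × 4 = 16, or 36%.
- On the Section 1.6 A list, with serving temperatures merged: 2 shared + 2 A-only + 4 B-only = 8. Pairs: 8 × 7 / 2 = 28. Crossing: 2 × 4 = 8, or 29%.
- Counting white bread as a further food gives 16 of 55 (29%) or 8 of 36 (22%).

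**Which pairs do not.** Every other pair can be compared within person in at least one panel. That covers each food against white bread, mix in water or muffin, and hot against room temperature. Cooking procedure can be compared within person among mix, waffle, pancake and muffin (A), and among mix, sponge cake, crispbread, smoothies and muffin (B). It crosses panels only for waffle or pancake against a B-only food.

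**Size, under an assumption.** The documents give no variance for the area under the curve and nothing on how panel choice relates to glucose response. I therefore assume a shift of δ SD between the people in the two panels, with no true food difference. For one unadjusted two-sample t test at a two-sided 0.05 with n per panel, the degrees of freedom are 2n − 2 and the noncentrality is δ√(n/2). With n = 10 and δ = 0.5, df = 18, the noncentrality is 0.5 × √5 = 1.118, and the rejection rate is 0.185.

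| Assumed shift (SD) | 10 v 10 | 5 v 5 |
|---|---|---|
| 0 | 5% | 5% |
| 0.25 | 8% | 6% |
| 0.5 | 19% | 11% |
| 0.75 | 36% | 18% |
| 1.0 | 56% | 29% |

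**Effect of anchoring to bread.** This was simulated (40,000 runs, 10 per panel, 0.5 SD shift, an assumed 60% of variance between persons).
- If the person effect carries over fully to the test food, the raw bias is 0.50 SD with 18% false positives. Subtracting each person's bread value removes the bias and gives 5%.
- If the test food carries only 60% of the person effect, the raw bias is 0.30 SD with 13% false positives. After anchoring, a bias of −0.20 SD and 7% remain.

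Anchoring thus removes an additive difference between persons, but not a different response to food among those who chose a panel.

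**After random allocation.** The expected shift is 0 and the rate is 5%. Chance imbalance remains: the standard error of the between-panel mean difference is √(2/10) = 0.45 SD at 10 v 10 and √(2/5) = 0.63 SD at 5 v 5.

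**The case against.** The strongest reply is that the plan never expressly schedules a test of an A-only food against a B-only food. The lead hypothesis compares supplemented food with white bread, which both panels eat. Section 1.6 A can be read as each food against bread. The inter-group comparisons in Section 6.1 A may well mean the glycemic groups. This stands in part: cross-panel testing is a possibility the plan leaves open, not one it declares. But a single food factor with Tukey's test, which by default compares all pairs, would produce those contrasts unless the plan excludes them.

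A second reply is that randomization buys little at this size. If 5 of 10 Prediabetes/Diabetes completers were diagnosed, a random 5/5 allocation would still give a 4–1 or more extreme split with probability 52/252 = 21%. That is correct, but chance imbalance is reflected in the standard error, whereas selection is not. Nor do the pilot label and the open statement that nobody is randomized remove the bias.

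Stronger readings are tempting, and the documents do not support them:
- A reader might infer that participants choose in the light of their glucose result. Section 1.3 gives the order of description, but does not say that they are told the value first. That they see the food lists is a fair inference, not a statement.
- A reader might infer that the bread comparisons, or the whole second hypothesis, are compromised. They can be made within panel, and serving temperature sits entirely in Panel A.
- A reader might take the 56% as the expected error. It needs a 1 SD shift arising within glycemic categories that the cell targets already balance, and a test without Tukey.

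**Conclusion.** The point holds in a limited form. Panel is self-selected, the planned analysis does not account for panel, and any A-only versus B-only contrast is open to selection bias: 16 of 45 supplemented pairs, or 8 of 28 on the Section 1.6 A list. Within-panel contrasts are unaffected provided they are made within person, which Section 6.1 A does not say. The size is unknown. The figure of about 19% false positives in place of 5% rests on an assumed 0.5 SD shift and a single unadjusted 10 v 10 test, and Tukey or bread anchoring would bring it down. This is an inexpensive improvement that should be made, not a flaw that undermines the pilot's main comparison with bread.

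**What to change.** In Sections 4.3 and 1.3, replace the participant's choice with random allocation to Panel A or B within each glycemic group. Reveal the panel only after eligibility, consent and group have been recorded. Existing staff can hold the list, preferably someone who does not screen. Apply the exclusion for "Self-reported allergy or intolerance to any ingredients in the test food" to the foods of both panels, so that everyone enrolled could take either.

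The cost is protocol wording and a short list, with enrolment still 24, completers still 20 and no extra visits. Participants lose their choice, which may slightly slow recruitment, and chance imbalance at 5 per cell remains.

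If choice is kept, state in Section 6.1 A that foods unique to different panels will not be tested directly against each other, and that each food is compared with the same person's white bread. That costs a sentence or two, and gives up the direct cross-panel comparisons.

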#### **4.4 Secondary Subjects**

N/A

#### **4.5 Number of Subjects**

##### **A. Total Number of Subjects**

24

##### **B. Total Number of Subjects If Multicenter Study**

N/A

**C. Require Number of Subjects to Complete Research**

20 (5 each in Panel A Non-Diabetes group and Prediabetes/Diabetes group, same two groups for Panel B)

**D. Feasibility Of Recruiting**

We expect to recruit the majority of our participants from the New Brunswick campus of Rutgers University. With a relatively flexible study schedule and no particularly stringent eligibility criteria, we do not anticipate difficulties in engaging interest in the Rutgers community. We expect a recruitment rate of 4-6 participants per week over 4-6 weeks including an estimated attrition rate of 20%.

